2.1.2 Primary endpoints

2.1.2.1 Part A

The primary endpoints for Part A of the trial are the MTD of BI 891065 and the number of patients with DLTs during the first treatment cycle. The MTD is defined as the highest dose with less than 25% risk of the true DLT rate being equal to or above 33%.

The primary endpoints of this part will be evaluated based on a timeframe from first treatment administration until the end of the MTD evaluation period (the end of the first cycle).

For doses below 25 mg, single patient cohorts will be treated at 5 mg and 15 mg if not specified otherwise by the SRC. A BLRM employing the EWOC principle will be used during the escalation phase for selection of doses to investigate and for estimation of the MTD. Cohorts of patients will receive escalating doses of BI 891065 until the MTD is reached or the highest possible dose has been tested. Each cohort will consist of newly enrolled patients. Estimation of the MTD during the escalation phase of the trial will be based upon the estimation of the probability of a DLT in Cycle 1 in the set of evaluable patients (where evaluable patients refer to patients not fulfilling the criteria for replacement [Section 3.3.4.4]) for the MTD. The corresponding methodology is described in Section 7 and in the statistical appendix (see Appendix 10.5). The MTD estimate established during the dose escalation of Part A will be re-investigated at the end of Part A by re-running the BLRM using the DLT information from all treatment cycles to determine the recommended dose range for Part B.

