3.3.4.1 Withdrawal from trial treatment

An individual patient is to be withdrawn from trial treatment(s) if:

- The patient wants to withdraw from trial treatment, without the need to justify the decision.
- The patient needs to take concomitant drugs that interfere with the investigational product or other trial medication.

- The patient can no longer be treated with trial medication for other medical reasons (such as surgery, adverse events, other diseases, or pregnancy [see Section 5.2.6.8]).
- The patient has been non-compliant with important trial procedures and, in the opinion of both, the Investigator and Sponsor representative, is not willing or able to stick to the trial requirements in the future.
- Recurring radiologic progression. Note: In the case of initial radiological PD, patients will be allowed to stay on treatment if the following criteria are met:
 - The Investigator feels that it is in the patient’s best interest
 - The patient signed an informed consent form specific for this circumstance after acknowledging that this practice is not considered standard in the treatment of cancer. The specific informed consent process for this circumstance includes discussion of alternative treatment options, including any available approved therapies (if applicable) and participation in alternative clinical trials.
 - Absence of clinical symptoms or signs indicating clinically significant PD
 - No decline in performance status
 - Absence of rapid PD or threat to vital organs or critical anatomical sites (e.g., central nervous system metastasis, respiratory failure due to tumour compression, spinal cord compression) requiring urgent alternative medical intervention
 - No significant, unacceptable, or irreversible toxicities related to study treatment.
- A pause of treatment or delayed start of treatment of more than 12 weeks due to SAEs/AEs
- The following adverse event(s) occur:
 - Cytokine release syndrome CTCAE Version 5.0 (R18-1357) Grade 3 or 4
 - Immune related AEs requiring permanent study drug discontinuation as described in Guidelines for Management of Immune-Related AEs (Appendix 10.2):
 - Grade 3 to 4 pneumonitis
 - Grade 3 to 4 adrenal insufficiency
 - Grade 4 diabetes mellitus
 - Any grade encephalitis
 - Grade 4 hypophysitis
 - Grade 4 rash
 - Grade 3 to 4 colitis or recurrent colitis of any grade
 - Any recurrent Grade 3 to 4 AE
 - Transaminase increases >5 times ULN or total bilirubin >3 times ULN

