3.3.4.3 Discontinuation of the trial by the Sponsor

Boehringer Ingelheim reserves the right to discontinue the trial overall or at a particular trial site at any time for the following reasons:

- Failure to meet expected enrolment goals overall or at a particular trial site
- Emergence of any efficacy/safety information invalidating the earlier positive benefit-risk-assessment that could significantly affect the continuation of the trial
- Violation of Good Clinical Practice (GCP), the trial protocol, or the contract, impairing the appropriate conduct of the trial.

The Investigator / the trial site will be reimbursed for reasonable expenses incurred in case of trial termination (except in case of the third reason).

3.3.4.4 Replacement of patients who have received at least one dose of BI 891065 or BI 754091

Replaced patients will not be evaluated for the MTD determination, and an additional patient will be entered at the same dose level. The following patients may be replaced:

- Patients who permanently discontinue treatment during treatment Cycle 1 of Part A or Part B for reasons other than a DLT, unless they develop a DLT.
- Patients who have missed more than 5 doses of BI 891065 in the first treatment cycle of Part A or Part B, unless they develop a DLT.
- Patients who have reduced BI 891065 dose level during treatment Cycle 1 Part A or Part B, unless they develop a DLT.
- Patients who have taken less than 80% of the BI 891065 overall dose during treatment Cycle 1 of Part B, unless they develop DLT.

- Patients who have received less than 50% of a BI 754091 initial dose of Part B, unless they develop a DLT.
- Patients who miss 2 or more partial or complete visits of the first cycle of Part A or Part B and (after discussion between the Sponsor and the Investigator) if the information needed to assess PK/PDc and safety parameters (including evaluation for DLTs), unless they develop a DLT.

Patients who permanently discontinue treatment because of a DLT will not be replaced.

Patients in the NSCLC expansion cohort (Part C) will not be replaced unless it becomes apparent that probably less than 40 patients will be evaluable for the assessment of the primary endpoint. In such a case, patients of the NSCLC expansion cohort concerned may be replaced only after confirmation of the Sponsor in writing.

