4.1.8 Definition of dose-limiting toxicity

Dose-limiting toxicities (DLTs) will be recorded throughout the trial. Any DLT must be reported to the [REDACTED] Medical Monitor by the Investigator or designee within 24 hours of first knowledge, and to the [REDACTED] as an SAE when appropriate. All DLTs will be agreed upon between the Sponsor, the Study Chair, the [REDACTED] Medical Monitor, and the Investigators after review of the data from each cohort. Only DLTs starting in the first cycle of monotherapy during Part A or during the first cycle of BI 891065 in combination with BI 754091 during Part B are necessary for dose-escalation decisions made by the SRC. DLT information from later cycles will be taken into consideration if available.

All relevant safety information (including DLTs) together with data on target engagement will be considered when selecting the recommended doses for the expansion cohorts.

Severity of AEs will be graded according to CTCAE Version 5.0. Any of the following AEs will be classified as DLTs following review by the Investigators and the [REDACTED] Medical Monitor unless unequivocally due to underlying malignancy or an extraneous cause.

Haematologic toxicities:

- For patients with solid tumours:
 - Any Grade 5 toxicity
 - Neutropenia \geq Grade 4 lasting for >5 days
 - Febrile neutropenia of any duration (ANC $<1.0 \times 10^9$ cells/L and fever $\geq 38.5^\circ\text{C}$)
 - Neutropenia Grade 3 with documented infection
 - Grade 4 thrombocytopenia, or Grade 3 thrombocytopenia with bleeding or a requirement for platelet transfusions
 - Grade 4 anaemia unexplained by underlying disease.

Non-haematological toxicities:

- AST or ALT >3 times ULN and concurrent total bilirubin >2 times ULN without initial findings of cholestasis (e.g., findings consistent with Hy's law or the FDA definition of potential DILI)
- \geq Grade 4 AST or ALT of any duration
- Any \geq Grade 3 non-haematologic toxicity with the following exceptions:
 - Grade 3 irAE that resolves to \leq Grade 1 or to baseline with immunosuppressive therapy within 2 weeks
 - Grade 3 fatigue that persists <7 days
 - Grade 3 rash that resolves to \leq Grade 1 within 2 weeks
 - Grade 3 or 4 elevation in serum amylase and/or lipase that is not associated with clinical or radiographic evidence of pancreatitis
 - Grade 3 electrolyte abnormality that lasts <72 hours, is not clinically complicated, and resolves spontaneously or responds to conventional medical intervention

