10. APPENDICES

10.1 IMMUNE-RELATED ADVERSE EVENTS OF SPECIAL INTEREST

Table 10.1: 1 Immune-related adverse events of special interest*

Immune-related adverse events of special interest
Pneumonitis (reported as an irAE if \geq Grade 2)

 • Acute interstitial pneumonitis • Interstitial lung disease • Pneumonitis
Colitis (reported as an irAE if \geq Grade 2 or any grade resulting in dose modification or use of systemic steroids to treat the AE)

 • Intestinal obstruction • Colitis • Colitis microscopic • Enterocolitis • Enterocolitis haemorrhagic • Gastrointestinal perforation • Necrotizing colitis • Diarrhea
Endocrine (reported as an irAE if \geq Grade 3 or \geq Grade 2 and resulting in dose modification or use of systemic steroids to treat the AE)

 • Adrenal insufficiency • Hyperthyroidism • Hypophysitis • Hypopituitarism • Hypothyroidism • Thyroid disorder • Thyroiditis • Hyperglycaemia, if \geq Grade 3 and associated with ketosis or metabolic acidosis
Endocrine (reported as an irAE)

 • Type 1 diabetes mellitus (if new onset)

Table 10.1: 1 Immune-related adverse events of special interest (continued)

Hematologic (reported as an irAE if \geq Grade 3 or any grade resulting in dose modification or use of systemic steroids to treat the AE)
 
 • Autoimmune haemolytic anaemia • Aplastic anaemia • Thrombotic thrombocytopenic purpura • Idiopathic (or immune) thrombocytopenia purpura • Disseminated intravascular coagulation • Haemolytic-uraemic syndrome • Any Grade 4 anaemia regardless of underlying mechanism

Hepatic (reported as an irAE if \geq Grade 2, or any grade resulting in dose modification or use of systemic steroids to treat the AE)
 
 • Hepatitis • Autoimmune hepatitis • Transaminase elevations (ALT and/or AST)

Infusion Reactions (reported as an irAE for any grade)
 
 • Allergic reaction • Anaphylaxis • Cytokine release syndrome • Serum sickness • Infusion reactions • Infusion-like reactions

Neurologic (reported as an irAE for any grade)
 
 • Autoimmune neuropathy • Guillain-Barre syndrome • Demyelinating polyneuropathy • Myasthenic syndrome

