In case of prolonged steroid therapy or treatment with immunosuppressives consider the possibility of opportunistic infections and tuberculosis reactivation. Careful monitoring and consideration of administration of prophylactic antibiotics where appropriate are warranted.

Commonly, referral to experts in the management of organ-specific conditions is highly recommended, especially for irAEs grade 3 or grade 4, or irAEs where management is complex.

BI 754091 and BI 891065 should be permanently discontinued for immune related

- encephalitis, aseptic meningitis, transverse myelitis, or Guillain-Barre syndrome of any grade
- acquired thrombotic thrombocytopenic purpura of any grade
- myocarditis of any grade
- myasthenia gravis, peripheral neuropathy or autonomic neuropathy of grade ≥ 3
- myositis grade 2 with objective findings (see below), any myositis grade ≥ 3
- hepatitis grade ≥ 3 (transaminase >5 times ULN or total bilirubin >3 times ULN), recurrent hepatitis grade ≥ 2
- nephritis grade ≥ 3 , persisting grade 2 nephritis unresponsive to initial steroid therapy or worsening, and recurrent nephritis grade ≥ 2
- pneumonitis grade ≥ 3
- rash, bullous dermatoses, severe cutaneous adverse reaction, Stevens Johnson Syndrome, toxic epidermal necrolysis of grade 4, and recurrent rash grade ≥ 3
- colitis grade 4, and recurrent colitis of any grade
- uveitis, iritis, episcleritis of grade ≥ 3
- autoimmune-hemolytic anemia grade ≥ 2
- haemolytic uremic syndrome grade ≥ 3
- immune thrombocytopenia grade 4

- any recurrent irAE grade ≥ 3 ,
- inability to taper steroids to 10 mg or less prednisone or equivalent within 12 weeks, or
- persistent Grade 2-3 AEs that do not recover to Grade 1 or less within 12 weeks.

Dose adjustment of BI 754091 and BI 891065 besides interrupting or permanently discontinuing BI 754091 and BI 891065 are not allowed.

In rare situations when benefit and risk assessment is considered positive for a patient to continue BI 754091 and BI 891065 treatment despite guidance to permanently discontinue (e.g. in case no alternative anti-cancer therapy is available), it should be discussed with the sponsor.

Pneumonitis:

- For Grade 1 pneumonitis with radiographic evidence of worsening, withhold BI 754091 and BI 891065 until improvement or resolution; BI 754091 and BI 891065 may be reintroduced upon radiographic improvement. In the absence of radiographic improvement within 3-4 weeks, follow guidance as for grade 2 event.

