- For Grade 2 hepatitis (AST/ALT 3–5x ULN and/or total bilirubin >1.5 to ≤ 3x ULN), BI 754091 and BI 891065 should be suspended. Monitoring of liver values every 3 days is recommended. Initiate treatment according to available guidelines. Restarting of BI 754091 and BI 891065 may be considered upon recovery to grade 1 or less, and on corticosteroid ≤ 10 mg per day.
- For Grade 3 or higher hepatitis, BI 754091 and BI 891065 has to be permanently discontinued.

Nephritis:

- For Grade 1 nephritis, consider temporarily withholding BI 754091 and BI 891065.
- For Grade 2 nephritis, withhold BI 754091 and BI 891065. Consult nephrology. Initiate treatment according to guidelines. In case of no improvement or worsening, permanently discontinue BI 754091 and BI 891065. BI 754091 and BI 891065 may only be re-started upon recovery to grade 1 or less, and on corticosteroid ≤ 10 mg per day.

- For Grade 3 or higher nephritis, permanently discontinue BI 754091 and BI 891065. Consult nephrology. Treat with steroids 1-2 mg/kg prednisone or equivalent. If improved to grade 1 or less, taper corticosteroids over no less than 4-6 weeks.
- BI 754091 and BI 891065 should also be permanently discontinued for recurrent nephritis grade 2 or higher.

Rash

- For Grade 1 rash, continue BI 754091 and BI 891065. Initiate topical treatment.
- For Grade 2 rash, BI 754091 and BI 891065 may be continued, in case of no improvement upon weekly monitoring, consider interruption of BI 754091 and BI 891065 therapy. Treat topically, add systemic corticosteroid therapies as clinically appropriate.
- For Grade 3 rash, withhold BI 754091 and BI 891065. Initiate topical and systemic therapy as per available guidelines. Upon improvement of event to grade 1 or less, and on corticosteroid ≤ 10 mg per day, consult with dermatology whether therapy with BI 754091 and BI 891065 might be restarted, especially in case no alternative anti-neoplastic therapy is available.
- For Grade 4 rash, BI 754091 and BI 891065 should be permanently discontinued.
- BI 754091 and BI 891065 should also be discontinued for recurrent rash grade 3 or higher.

Bullous dermatosis

- For Grade 1 bullous dermatosis, use local wound care and observation. BI 754091 and BI 891065 can be continued.
- For Grade 2 bullous dermatosis, withhold BI 754091 and BI 891065. Administer topical therapy, add systemic therapy as clinically adequate.

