6.3 SUBJECT SETS ANALYSED

The Screened Set (SCR) includes all patients who signed the informed consent form and will be used to summarise patient disposition.

The Enrolled Set (ES) includes all patients who have been enrolled into the study and will be used for demographics analyses.

The Treated Set (TS) consists of all patients who have received at least one administration of any trial medication and will be used for all planned safety, efficacy and biomarker analyses in the CTRs besides the MTD determination.

The MTD Evaluation Set includes all patients from the TS who have not been replaced for the MTD evaluation; patients who has no actual replacement but satisfies the replacement criteria per protocol thus ineligible for MTD evaluation will also be excluded form the MTD Evaluation set. This set will be used for the primary analyses of DLTs and MTD determination.

Rules for replacement of patients are defined in CTP Section 3.3.4.4. The list of patients replaced for MTD evaluation or ineligible for MTD evaluation will be stored in the trial master file.

The Pharmacokinetic Parameter Set (PKS) consists of all patients in the TS who have at least one valid secondary PK endpoint available and will be used for all pharmacokinetic analyses.

[figure not shown]
The ECG Set includes all patients in the treated set who do not have an artificial pacemaker and have at least one on-treatment value for at least one ECG variable.

The ECG Pharmacokinetic Concentration Set (ECGPCS) includes all patients from the ECG Set who provide at least one time-matched pair of valid BI 891065 plasma concentration and corresponding ECG variable to be used in the exposure-response analysis.

The decision about concentration value validity needs to be made within the Clinical Pharmacology group. Refer to the [Section 7.8.4](#) for the definition of the maximum acceptable

time deviation between PK blood sampling and ECG recording at different time points during the trial.

The analysis of ECG data will be based on the ECG Set, except those analyses concerning the relationship between plasma concentrations and ECG variables which will be based on the ECGPCS. Listings for patients with artificial pacemakers will be based on the TS.

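### Some Cycle 1 toxicities that oblige permanent discontinuation can fall outside the DLT definition, so the patient leaves the MTD Evaluation Set and is an event in neither BLRM run

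*Protocol*

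**What the plan says.** **What counts as a DLT (Protocol 4.1.8).** A Grade 3 irAE is exempt when it resolves to ≤ "Grade 1 or to baseline with immunosuppressive therapy within 2 weeks". Grade 4 neutropenia counts only beyond 5 days. Grade 3 or 4 amylase or lipase without evidence of pancreatitis is exempt. Below Grade 3, apart from a few named events, a toxicity counts only if it is treatment-related, at least Grade 2, persistent, and prevents BI 754091 on Cycle 2 Day 1. A closing sentence gives discretion over what is treated as a DLT, without a criterion.

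**What stops treatment for good.** Protocol 3.3.4.1 lists "Cytokine release syndrome CTCAE Version 5.0" at Grade 3 or 4, transaminases above 5 times ULN, and drug-related events of Grade 4 or higher. Protocol 10.2 adds "For Grade 3 or higher hepatitis, BI 754091 and BI 891065 has to be permanently discontinued". Table 10.1: 1 places CRS in the group headed "Infusion Reactions (reported as an irAE for any grade"), so the irAE exemption can reach it.

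**Who is evaluable.** Protocol 3.3.4.4 permits replacement of "Patients who permanently discontinue treatment during treatment Cycle 1 of Part A or Part B for reasons other than a DLT". Protocol 4.1.10 makes anyone who meets a replacement criterion non-evaluable. SAP 6.3 confirms that a patient without an actual replacement who "satisfies the replacement criteria per protocol thus ineligible for MTD evaluation will also be excluded".

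**What the model does.** "The MTD is defined as the highest dose with less than 25% risk of the true DLT rate being equal to or above 33" per cent (Protocol 2.1.2.1; 2.1.2.2 says the same for the combination). SAP 7.4 runs the BLRM twice: on first-cycle DLTs in the MTD Evaluation Set, and on all on-treatment DLTs in the treated set.

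**The concern.** The three sets of rules were evidently written for different purposes and do not meet. A patient whose drug-related toxicity obliges the investigator to stop treatment may have no DLT. That patient then counts as having stopped for another reason, as if for an administrative one.

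The number of patients with DLTs and the MTD are the primary endpoints of Parts A and B, and both come from the MTD Evaluation Set. Cohorts are small (5 to 8 evaluable patients per combination in Table 7.1.2: 5), so one or two patients can matter. The gap touches immune and cytokine effects, which the benefit-risk section (Protocol 1.4) singles out for the combination.

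**Working it through.** **Step 1. Do the rules overlap?**

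| Cycle 1 event | Permanent stop ordered by | DLT under 4.1.8? |
|---|---|---|
| Grade 3 CRS, resolved within 2 weeks on immunosuppression | 3.3.4.1, 5.2.6.4.3 | No, if treated as an irAE (Table 10.1: 1) |
| Immune-related Grade 3 transaminases above 5 times ULN, bilirubin criterion not met, resolved likewise | 3.3.4.1, 10.2 | No |
| Drug-related Grade 4 neutropenia of 5 days or less, uncomplicated | 3.3.4.1, 4.1.7 | No |
| Drug-related Grade 4 amylase or lipase, no evidence of pancreatitis | 3.3.4.1, 4.1.7 | No |

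The last two do not depend on irAE status and can arise in Part A. A further case, "myocarditis of any grade" (Protocol 10.2), turns at low grade on how the Cycle 2 Day 1 criterion is read.

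**Step 2. Direction.** Among all treated patients, let d be the proportion with a DLT and e the proportion with treatment-stopping toxicity that is not a DLT.
- The MTD Evaluation Set estimates d/(1 − e).
- Counting all treatment-stopping toxicity gives d + e.
- d/(1 − e) < d + e is equivalent to 0 < e(1 − d − e), true whenever e > 0 and d + e < 1.
- But d/(1 − e) > d: exclusion alone raises the estimated DLT rate.

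The documents give no value for e. Assuming 5% to 10%:
- d = 0.25, e = 0.10: 0.25/0.90 = 0.278 modelled, against 0.350.
- d = 0.30, e = 0.05: 0.30/0.95 = 0.316 modelled, against 0.350.

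In both, the modelled rate lies in the target interval and the combined rate lies above 0.33.

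**Step 3. Reproduce the plan's figures.** The model is that of Protocol 7.1.2: odds(π12) = odds(π1 + π2 − π1π2) × exp(η · d1/200 · d2/d2*). Draws from the printed mixture priors were weighted by the binomial likelihood. The printed reference dose d2* = 3200 mg does not reproduce the tables; 240 mg does, and is used here as an assumption.
- Table 10.5: 11, 100/240 with 0/3, 1/3, 2/3 (Table 10.5: 8 prior): 0.013, 0.065, 0.257; printed 0.012, 0.066, 0.256.
- Table 7.1.2: 6, 400/240 (0/6, 0/8, 1/5; Table 10.5: 7 prior, because the updated prior is not printed): 0.073; printed 0.072. The lower-dose rows agree less closely (at 200 mg q.d., 0.882 below 0.16 against 0.853 printed).
- Scenario 5, next dose 400/240: 0.237; printed 0.234.

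**Step 4. Add hypothetical patients at 400/240, current Part B data.**

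| Handling | Data | P(overdose) |
|---|---|---|
| One patient kept as a non-event | 1/6 | 0.050 |
| Excluded, as planned | 1/5 | 0.073 |
| One counted as an event | 2/6 | 0.194 |
| Two counted as events | 3/7 | 0.363 |

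In Scenario 5, one such patient counted at 200/240 (1/5) moves 400/240 from 0.237 to 0.393.

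**Step 5. Sensitivity of 1/5, 2/6, 3/7.** The Table 10.5: 8 prior gives 0.107, 0.254, 0.438, but it assumes a DLT at 400 mg in Part A, where 0/6 was observed. The printed 3200 mg with the Table 10.5: 7 prior gives 0.039, 0.107, 0.230. In Part A at 400 mg, 0/6, 1/7 and 2/8 give 0.004, 0.038 and 0.136.

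**The case against.** The strongest reply is that nothing is concealed. Protocol 4.1.3.2 puts all Grade 2 or higher toxicity in the evaluation period before the SRC, and 4.1.4 brings adverse events that are not DLTs into dose decisions. The SRC, not the model, determines the MTD, DLTs are jointly adjudicated under 4.1.8, and 3.3.4.5 can halt enrolment. All of this stands. It protects dose decisions, but it does not define what enters the model or the reported endpoint.

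Second, excluding a non-DLT patient is conservative for the DLT rate as defined: 0.073 against 0.050. This also stands. The larger shifts in Step 4 come wholly from reclassifying the patient as an event.

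Third, the overlap is narrower than the stopping list suggests:
- CRS is listed apart from immune-related events in 3.3.4.1 and has its own AESI section, so its exemption is arguable, though Table 10.1: 1 supports it.
- Raised transaminases with bilirubin above 2 times ULN without cholestasis, and Grade 4 transaminases, are DLTs in their own right.
- Amylase and lipase are tested only when there are symptoms of pancreatitis (5.2.3), so that case will be rare.
- Uveitis does not belong here: 4.1.8 counts even Grade 2 related uveitis that needs systemic treatment.

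The remaining cases are enough to show the gap.

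**Conclusion.** The gap is in the text and affects both BLRM runs. Without discretionary adjudication, a patient with one of these toxicities is absent from the first run and a non-event in the second. Relative to treatment-stopping toxicity, the model input is too low whenever such patients occur.

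Three stronger readings go beyond the documents:
- **That the replacement rule lowers the DLT rate.** It raises the rate as defined.
- **That these patients are always replaced.** Replacement is permissive; only exclusion from the MTD Evaluation Set is fixed.
- **That one such patient would overturn the current dose conclusion, or that a past decision was wrong.** On the current data one added event gives 0.19 and still passes EWOC; two give 0.36 and fail. The reversal by a single patient is in Scenario 5, a hypothetical already near the limit. No such patient is reported.

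The size in this trial is therefore unknown. The figures rest on the Table 10.5: 7 prior (Table 10.5: 8 for Scenario 5) and on a 240 mg reference dose. With the printed 3200 mg, even two added events stay below 0.25, but that value does not reproduce the plan's tables.

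**What to change.** **(a) Sensitivity run.** In SAP 7.4, pre-specify a further BLRM run for Parts A and B. It should keep in the set, and count as an event, every patient whose drug-related Cycle 1 toxicity meets a permanent-discontinuation criterion mandated by the protocol. A voluntary stop for a low-grade event should not qualify. Supply the result to the SRC and show it beside the two planned runs, with the number of patients concerned.

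**(b) Reconciliation.** Reconcile 4.1.8 and 3.3.4.4 with 3.3.4.1, 4.1.7 and 10.2, so that the documents say whether such events are DLTs and whether the patients are evaluable. Which clinical rule applies is for the sponsor. The same pass should settle three other discrepancies:
- 3.3.4.1 and 10.2 differ on Grade 3 colitis and on Grade 3 to 4 adrenal insufficiency.
- 4.1.7 and 5.2.6.4.2 differ on which drugs stop after a Grade 3 infusion reaction.
- The printed BI 754091 reference dose does not match the Part B tables.

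**Cost.** One extra model run on data already collected and a few sentences of text. The dose recommendation may become more conservative if such patients exist.
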